5.1.8.6. Physical Exams

The number and percentage of patients with new-onset abnormal physical examinations will be summarized by body system by visit based on the SAF-LTS.

5.1.8.7. Joint Pain Questionnaire

The number and percentage of patients with significantly worse joint pain will be summarized by visit and joint based on the SAF-LTS.

5.1.8.8. Arthropathy Adjudications

The number and percentage of patients with images requiring arthropathy adjudication as well as the number and percentage of those patients with confirmed adjudicated arthropathy will be summarized by based on the SAF-LTS. Subtypes of AAs and outcomes of AAs will also be summarized. Patient listings of cases confirmed by adjudication will be provided.

5.1.8.9. Neurological Exam

The number and percentage of patients with new-onset abnormal neurological examinations will be summarized by Neurological evaluations by visit based on the LTS-SAF.

5.1.8.10. Analysis of Pharmacokinetics and Drug Concentration Data

Summaries of concentrations of functional fasinumab will be presented by nominal time point and dose. Plots of mean or median concentration of functional fasinumab will be presented by nominal day and dose.

5.1.9. Analysis of Anti-Drug Antibody Data

The ADA variables described in Section 4.7 will be summarized using descriptive statistics by dose/cohort group in the ADA analysis set. Prevalence of treatment-emergent and treatment-boosted ADA will be assessed as absolute occurrence (N) and percent of patients (%), grouped by study cohorts. For treatment emergent ADA, occurrence (N) and percent of patients (%) with persistent, transient and indeterminate ADA will be reported. The influence of treatment-emergent or treatment-boosted ADA assay response on individual PK profiles may be evaluated.

Listings of ADA positivity and titers presented by patient, time point, and dose cohort/group will also be provided.

Correlation analysis of safety versus treatment-emergent ADA positivity status may be performed on the SAF. Assessment will focus on the following safety events:

- Hypersensitivity (SMQ: Hypersensitivity [Narrow])
- Anaphylaxis (SMQ: Anaphylaxis[Narrow])

Number (%) of patients with the above-mentioned safety events may be summarized by treatment-emergent ADA positivity status, during the TEAE period.

In addition, correlation analysis of key efficacy endpoints versus treatment-emergent ADA status in patients who discontinued due to lack of efficacy may be summarized.

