#### 9.5.5. Descriptive Analysis of Anti-Drug Antibody Data

Listings of ADA positivity and titers presented by patient, time point, and dose group will be provided. Prevalence of treatment-emergent and treatment-boosted ADA response will be assessed as absolute occurrence (N) and percent of patients (%), grouped by study cohorts.

The influence of ADAs on drug concentrations will be evaluated. Assessment of impact of ADAs on safety and efficacy may be provided.

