1. OVERVIEW

The purpose of the Statistical Analysis Plan (SAP) is to ensure the credibility of the study results by pre-specifying the statistical approaches for the analysis of study data prior to database lock. The SAP is intended to be a comprehensive and detailed description of the definitions and statistical methods to be used in the analysis of data for study R475-PN-1523.

This plan may be revised during the study to accommodate protocol amendments and/or to make changes to adapt to unexpected issues in study execution and/or data that affect planned analyses. These revisions will be based on blinded review of the study and data, and a final plan will be issued prior to the first step database lock and before unblinding of the study.

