3.5. The Anti-drug antibody Analysis Set

The ADA analysis set includes all treated patients who received any treatment and who had at least 1 non-missing post-dose ADA result.

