4.7. Anti-Drug Antibody Variables

Samples for Anti-Drug Antibody (ADA) evaluation will be collected at baseline and at subsequent study visits.

Anti-drug antibody variables will include ADA status (positive or negative) and titer as follows:

- Total subjects negative in the ADA assay at all time points analyzed
- Pre-existing immunoreactivity - a positive ADA response at baseline with all post-dose ADA results negative, or a positive ADA response at baseline with all post-dose ADA responses less than 9-fold over baseline titer levels.
- Treatment emergent - defined as any post-dose positive ADA response when baseline results are negative
 - Persistent - A positive result in the ADA assay detected in at least 2 consecutive post baseline samples separated by at least a 16-week post baseline period [based on nominal sampling time], with no ADA-negative results in-between, regardless of any missing samples
 - Indeterminate - A positive result in the ADA assay at the last collection time point analyzed only, regardless of any missing samples

- Transient - Not persistent or indeterminate regardless of any missing samples
- Treatment boosted - defined as any post-dose positive ADA response that is at least 9-fold over the baseline level when baseline is positive in the ADA assay
- Titer Values
- Titer category: low (titer <1,000); moderate ($1,000 \leq \text{titer} \leq 10,000$); high (titer >10,000)
- Neutralizing ADA activity for samples positive in the ADA assay

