- H₂₃: There is no treatment difference between fasinumab 1 mg Q8W and placebo in the proportion of patients with $\geq 30\%$ improvement in the WOMAC pain subscale scores at week 16 versus there is a treatment difference in proportion of patients with $\geq 30\%$ improvement in WOMAC pain at week 16

The estimand for the primary efficacy objective is the difference in means between each fasinumab dose+protocol-defined rescue medication and placebo+protocol-defined rescue medication in the change from baseline to week 16 in the WOMAC pain and physical function scores in the FAS-substudy, regardless of whether or not prohibited medication had been taken. Data collected after discontinuing treatment up to week 16 will not be used in the primary efficacy analysis but used in a treatment policy sensitivity analysis. The missing data for patients who discontinued treatment due to lack of efficacy or AEs will be imputed with values centered at the mean baseline value of the treatment group that patients were randomized to. The missing data for patients discontinued treatment due to other reasons will be imputed under missing-at-random assumption using the regression method with adjustment for covariates including treatment group, randomization strata, and baseline score. Intermittently missing data will be imputed using Markov Chain Monte Carlo method.

The primary efficacy variables will be analyzed using a multiple imputation approach with mixed-effect model for repeated measure (MMRM) based on the FAS-substudy with adjustment for missing data due to treatment discontinuation for the reasons of lack of efficacy or AEs assuming the WOMAC scores would on average return to baseline values. Missing data up to week 16 will be imputed 50 times to generate 50 complete data sets by using the SAS procedure PROC MI following the 3 steps below:

- Step 1: The monotone missing pattern is induced by Markov Chain Monte Carlo (MCMC) method in MI procedure using seed number [REDACTED]
- Step 2: The missing data at subsequent visits will be imputed using the regression method for the monotone pattern with seed number [REDACTED] and adjustment for covariates including treatment groups, randomization strata, relevant baseline and all values at preceding visits.

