Each imputed data set will be analyzed using the MMRM model with treatment, randomization strata, and relevant baseline included in the model. For each δ the SAS MIANALYZE procedure will be used to generate valid statistical inferences by combining results from the 50 analyses using Rubin's formula. By progressively increasing δ , the sensitivity analysis will explore the tipping points, e.g., δ value when the p-value for a treatment comparison is above 0.0167, 0.0333 or 0.05. Results will be then summarized using summary tables and graphs.

Per Protocol Set Analysis

Sensitivity analyses based on the PPS will be performed using the MMRM approach.

Subgroup Analysis

Descriptive analyses will be performed on the primary endpoints and key secondary endpoint of PGA to summarize the treatment effects across subpopulations defined by baseline randomization strata (index joint and K-L score category), demographics (age group, sex, race) and baseline characteristics (weight and BMI categories). Subgroup analysis based on other medical conditions may also be performed. Forest plots for the subgroup analysis will be provided.

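### The only ADA-versus-efficacy analysis specified in the SAP is confined to patients who stopped for lack of efficacy, so it selects on the outcome and attenuates any antibody-related loss of effect

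*SAP*

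**What the plan says.** SAP 5.1.9 offers two optional analyses of ADA against outcomes.

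- **Safety:** "Correlation analysis of safety versus treatment-emergent ADA positivity status may be performed on the SAF", that is, on all treated patients.
- **Efficacy:** "correlation analysis of key efficacy endpoints versus treatment-emergent ADA status in patients who discontinued due to lack of efficacy may be summarized".

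No other SAP section relates ADA to efficacy. The subgroup paragraph in SAP 5.2.7.1.2 will "summarize the treatment effects across subpopulations defined by baseline randomization strata", demographics and baseline characteristics, and does not name ADA status.

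The protocol is wider. Section 9.5.5 says "Assessment of impact of ADAs on safety and efficacy may be provided", with no population and no method. SAP 1.2.4, which lists departures from the protocol, does not mention the narrowing. SAP section 1 says of itself: "The SAP is intended to be a comprehensive and detailed description of the definitions and statistical methods".

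Two definitions matter. SAP 3.5: "The ADA analysis set includes all treated patients who received any treatment and who had at least 1 non-missing post-dose ADA result". SAP 4.7: "Treatment emergent - defined as any post-dose positive ADA response when baseline results are negative". The second has no time limit. ADA is sampled at baseline and weeks 16, 32, 52 and 72, and at early termination (Protocol 6.1, Tables 1, 2 and 4), so a sample taken after week 16 can set the status that is compared with a week 16 endpoint.

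**The concern.** If antibodies reduce the drug's effect, two signs are expected: worse week 16 scores in ADA-positive patients across the sub-study, and more lack-of-efficacy stops among them. Within the SAP's subset everyone has already failed treatment. The first sign is therefore attenuated by selection, and the second cannot be estimated from the subset alone because the patients who did not stop are left out.

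Missing-data handling adds to this for stops before week 16. SAP 5.2.7.2 counts a missing responder status as non-response. For WOMAC, SAP 5.2.7.1.1 says that missing values after such a stop "will be imputed with values centered at the mean baseline value of the treatment group" to which the patient was randomized, and ADA status is not among the imputation covariates.

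At stake is the reading of immunogenicity. A weak or absent difference in this subset says little about whether antibodies matter, yet it would be the one ADA-efficacy result that the SAP describes.

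**Working it through.** **Inputs from the documents.** SAP 2.2: 200 patients per arm, 15% dropout, effect size 0.46 (WOMAC) and 0.36 (Patient Global Assessment), two-sided 0.0167. SAP 2.1: allocation 1:1:1:1:1, so 400 patients in the two 1 mg arms and 800 in the four fasinumab arms.

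**Assumptions, because the documents give no figure.** ADA-positive 2 to 10%. Stopping for lack of efficacy 3 to 7.5%, within the 15% total dropout. ADA removes the full 0.46 SD.

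**Step 1: the plan's own figure.** The ADA section states none. The nearest is the sub-study power. Evaluable per arm: 200 × 0.85 = 170. Power = Φ(d√(170/2) − 2.393).
- d = 0.46: Φ(4.241 − 2.393) = 0.968; the plan says at least 96%.
- d = 0.36: Φ(3.319 − 2.393) = 0.823; the plan says at least 82%.

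Both reproduce. They supply inputs and do not bear on the ADA question.

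**Step 2: attenuation by selection.** Let higher change mean a worse score, N(0, 1) without ADA and N(0.46, 1) with ADA. If stopping is decided by the outcome itself, patients above a threshold c stop, where

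(1 − p)[1 − Φ(c)] + p[1 − Φ(c − 0.46)] = L,

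with p the ADA-positive share and L the stopping rate. The mean among stoppers is μ + φ(c − μ)/[1 − Φ(c − μ)].

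Example with p = 10%, L = 5%: c = 1.708; means 2.188 with ADA and 2.118 without; difference 0.07 SD against a true 0.46.

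If stopping only correlates with the outcome (simulation of 4 million patients, p = 10%, L = 5 to 7.5%):

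| Correlation of stopping with outcome | Difference among stoppers |
|---|---|
| 1.0 (formula, p 5–10%, L 3–7.5%) | 0.06–0.08 SD |
| 0.8 | about 0.22 SD |
| 0.5 | about 0.36 SD |

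**Step 3: numbers of patients (two 1 mg arms).**
- Stoppers: 400 × 0.03 = 12 to 400 × 0.075 = 30.
- ADA-positive among them, if ADA is unrelated to stopping: 12 × 0.02 = 0.24 to 30 × 0.10 = 3.
- ADA-positive among them, if ADA (5 to 10%) removes the effect and the outcome decides stopping: about 1.5 to 6.
- ADA-positive without the restriction: 400 × 0.02 = 8 to 400 × 0.10 = 40, giving 25% to 79% power for 0.46 SD at two-sided 0.05, pooling the two arms and ignoring missing data. Per arm the count is 4 to 20.

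**Step 4: the discontinuation rate.** In the Step 2 example, 1 − Φ(1.708 − 0.46) = 10.6% of ADA-positive and 1 − Φ(1.708) = 4.4% of ADA-negative patients stop, a ratio of about 2.4. The subset alone shows only that 0.10 × 10.6% / 5% = 21% of stoppers are ADA-positive.

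**Step 5: stops before week 16 with missing values.**
- Responder endpoint: ADA-positive and ADA-negative patients are all non-responders, so the contrast is zero.
- WOMAC: Step 2 of the SAP algorithm regresses on earlier visits. Step 3 subtracts one constant k for the arm and visit. Since (a − k) − (b − k) = a − b, Step 3 leaves differences between patients unchanged. What survives is the part of the ADA difference carried by earlier scores. A simulation of both steps (stop after week 8; 5 to 10% ADA-positive; 5 to 10% stopping; stopping driven by the week 8 or week 16 score plus noise of SD 0.7) left about 0.09 to 0.26 SD. The between-visit correlation was assumed: exchangeable 0.6 to 0.7, or first-order autoregressive 0.7 to 0.8. In most settings this was below the unimputed difference in the same patients, in a minority slightly above it, and never zero.

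**The case against.** The best defence has four parts.

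**The sentence is optional and descriptive.** No primary, key secondary or multiplicity-controlled result uses it. This stands and limits the weight of the point.

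**The protocol keeps a wider assessment open.** Section 9.5.5 has the same optional status and no restriction. It also commits to evaluating the influence of ADA on drug concentrations. A reader might infer that the restricted correlation is the only ADA-efficacy analysis planned anywhere. That is too strong: it is the only one specified in the SAP.

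**The imputation does not erase the contrast.** A reader might take centring at the baseline mean to give ADA-positive and ADA-negative stoppers the same expected WOMAC value. Step 5 shows otherwise. Also, the sentence has no week 16 limit and dosing runs to week 48, so a patient who stops after week 16 can have an observed week 16 score. SAP 5.1.9 does not say that imputed values would be used.

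**The discontinuation signal is not wholly lost.** SAP 5.1.9 firmly plans ADA prevalence by cohort and patient listings. Because P(ADA+ | stop)/P(ADA+) = P(stop | ADA+)/P(stop), a reader could set 21% among stoppers beside 10% overall in the example and recover the twofold excess. The route is indirect, since the prevalence is not stated for the sub-study up to week 16.

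None of this gives a reason to restrict the efficacy comparison to treatment failures when the safety comparison in the same section uses all treated patients.

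**Conclusion.** The point holds in a limited form. The SAP states a rule that conditions on the outcome, leaves out the comparison patients, and is narrower than Protocol 9.5.5 without being listed as a change. A true 0.46 SD difference would appear as roughly 0.06 to 0.36 SD, in a subset with about 0.2 to 6 ADA-positive patients over two arms. For stops before week 16 with missing data, the responder contrast disappears, and the WOMAC contrast is attenuated, usually further than by selection alone, but not to zero.

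The size depends on assumed ADA and stopping rates, a full loss of effect, and the link between stopping and outcome. The direction requires only that stopping for lack of efficacy is related to the efficacy score. A stronger inference, that the analysis would produce false reassurance, is not supported: so few ADA-positive patients could not support a firm statement either way.

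**What to change.** In SAP 5.1.9:

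1. Replace the restricted sentence with a summary of the co-primary and key secondary endpoints at week 16 by treatment-emergent ADA status, in all sub-study patients in the ADA analysis set, by treatment arm.
2. For this summary, take ADA status from post-dose samples up to and including week 16, including earlier end-of-treatment or early-termination samples.
3. Tabulate the proportion discontinuing for lack of efficacy by ADA status.
4. Keep the discontinuer-only summary as a supplement.

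This also brings the SAP back into line with Protocol 9.5.5. The cost is a short SAP edit and one extra table. No new samples are needed, since ADA is already drawn at baseline and week 16. The limits remain: few ADA-positive patients, and an ADA status that arises after randomisation, so the output stays descriptive and cannot establish cause.

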5.2. Statistical Methods for Efficacy Sub-Study

5.2.1. Demographics and Baseline Characteristics

Demographic and baseline characteristics will be descriptively summarized by treatment group, combined fasinumab, and overall based on the FAS-substudy. Parameters to be summarized include those described in Section 4.1.

5.2.2. Medical History

Medical history will be descriptively summarized by treatment group, combined fasinumab, and overall based on the FAS-substudy.

5.2.3. Prior / Concomitant Medications

Prior Medications

All prior medications, dictionary coded by WHO, will be descriptively summarized by treatment group, and combined fasinumab based on the FAS-substudy similar to the summary for FAS-LTS.

Concomitant Medications

All concomitant medications, dictionary coded by WHO, will be descriptively summarized by treatment group, and combined fasinumab based on the SAF-substudy similar to the summary for FAS-LTS.

5.2.4. Prohibited Medications

Number and percentage of patients with prohibited medications will be descriptively summarized by treatment group, and combined fasinumab based on the SAF-substudy.

The number of patients with NSAID use during treatment period 1 will be summarized by treatment group, and combined fasinumab.

5.2.5. Patient Disposition

The disposition of patients in the sub-study will be summarized by treatment group, combined fasinumab, and overall for FAS-Substudy.

- Unless otherwise noted, percentages will be calculated using the number of patients randomized in FAS-substudy as the denominator. This will be summarized by treatment group, combined fasinumab, and overall for the efficacy sub-study. Kaplan-Meier plot of time to treatment discontinuation will be provided. Summaries will provide the frequency (and percentage as applicable) of patients that met the criteria for the following variables:
- Patients randomized (defined as having received a randomization number). This row will reflect grouping based on randomization assignment.
- Patients randomized but not treated. This row will reflect grouping based on randomization assignment.
- Patients randomized and treated.
- Patients who completed treatment period 1. Reason for treatment discontinuation during the efficacy sub study and efficacy sub-study withdrawal will be provided.

5.2.5.1. Analysis Set

Summary of the number (and percentage) of patients in each analysis set will be by treatment group, combined fasinumab, and overall for the efficacy sub-study.

Additionally, the following listings will be provided (if applicable):

- Listing of Patients Treated but not Randomized.
- Listing of Patients Randomized but not Treated.

- Listing of Patients Randomized but not Treated with the Randomized treatment.
- Listing of Patient Disposition for all Randomized Patients.
- Listing of Screening Failures and reasons for all screen failed patients.

5.2.6. Extent of Study Treatment Exposure and Compliance

The analysis population for the efficacy sub-study is based on the SAF-substudy.

5.2.6.1. Measurement of Treatment Compliance

Compliance with protocol-defined investigational product will be calculated by treatment group and combined fasinumab as follows:

$$\frac{(\text{Number of actual injections of study drug during the efficacy sub-study exposure period})}{(\text{Number of planned injections of study drug during the efficacy sub-study exposure period on or before the time that the patient discontinues from the efficacy sub-study})} \times 100\%$$

Treatment compliance will be presented by descriptive statistics as well as the number (%) of patients who have:

- 1, 2, 3, and 4 SC injections (for the efficacy sub-study)

5.2.6.2. Exposure to Investigational Product

The treatment exposure to fasinumab and placebo SC doses will be calculated as:

- $(\text{Date of last efficacy sub-study drug dose} - \text{date of first study drug dose}) + 28$

The duration of exposure in will be summarized for each treatment group using the number of patients (n), mean, standard deviation, median, Q1, Q3, minimum, and maximum.

The number (%) of patients with exposure duration periods will be presented by specific time periods. The time periods of interest are specified as: ≥ 1 day, ≥ 29 days, ≥ 57 days, and ≥ 85 days

5.2.6.3. Length of sub study Observation

The length of the sub study observation (days) will be calculated as: $(\text{Date of last efficacy sub-study visit [up to week 16]} - \text{date of first study drug dose}) + 1$

The observation duration will be summarized for each treatment group using the number of patients (n), mean, standard deviation, median, Q1, Q3, minimum, and maximum.

The number (%) of patients with observation periods will be presented by specific time periods. The time periods of interest are specified as: ≥ 1 day, ≥ 29 days, ≥ 57 days, ≥ 85 days, and ≥ 113 days

5.2.6.4. Protocol Deviations

Protocol deviations will be summarized for patients incurring any major deviation by count and percentage, and patients incurring each type of major deviation by count and percentage for FAS-Substudy. Protocol deviations leading to exclusion from the PPS for the efficacy sub-study (see Section 3.3 for definition) will be summarized for any patients incurring any such deviation by count and percentage, and patients incurring each type of deviation by count and percentage.

5.2.7. Analysis of Efficacy Data

5.2.7.1. Analysis of Primary Efficacy Variable(s)

5.2.7.1.1. Primary Efficacy Analysis

The co-primary efficacy endpoints in the efficacy sub-study are:

- Change from baseline to week 16 in the WOMAC pain subscale score
- Change from baseline to week 16 in the WOMAC physical function subscale score

The primary treatment comparison for the WOMAC pain subscale score as well as the WOMAC physical function subscale score is declared superior only if the comparisons are significant for both WOMAC pain and physical function subscale scores at any of the allowed doses. Hence there are 6 hypotheses to be tested between the primary and key secondary endpoints. A hierarchical procedure will be used to control the overall Type-1 error rate at 0.05 for the 2 co-primary endpoints and the secondary endpoints across the 2 dose regimens. Each hypothesis will be formally tested only if the preceding one is significant at the 2-sided 0.05 significance level. The hierarchical testing order for the 6 hypothesis is as follows:

- H_{11} : There is no treatment difference between fasinumab 1 mg Q4W and placebo in WOMAC pain or physical function subscale scores at week 16 versus there is a treatment difference in WOMAC pain and physical function subscale scores at week 16
- H_{12} : There is no treatment difference between fasinumab 1 mg Q4W and placebo in Patient Global Assessment score at week 16 versus there is a treatment difference in Patient Global Assessment score at week 16
- H_{13} : There is no treatment difference between fasinumab 1 mg Q4W and placebo in the proportion of patients with $\geq 30\%$ improvement in the WOMAC pain subscale scores at week 16 versus there is a treatment difference in proportion of patients with $\geq 30\%$ improvement in WOMAC pain at week 16
- H_{21} : There is no treatment difference between fasinumab 1 mg Q8W and placebo in WOMAC pain or physical function subscale scores at week 16 versus there is a treatment difference in WOMAC pain and physical function subscale scores at week 16

- H₂₂: There is no treatment difference between fasinumab 1 mg Q8W and placebo in Patient Global Assessment score at week 16 versus there is a treatment difference in Patient Global Assessment score at week 16
- H₂₃: There is no treatment difference between fasinumab 1 mg Q8W and placebo in the proportion of patients with $\geq 30\%$ improvement in the WOMAC pain subscale scores at week 16 versus there is a treatment difference in proportion of patients with $\geq 30\%$ improvement in WOMAC pain at week 16

The estimand for the primary efficacy objective is the difference in means between each fasinumab dose+protocol-defined rescue medication and placebo+protocol-defined rescue medication in the change from baseline to week 16 in the WOMAC pain and physical function scores in the FAS-substudy, regardless of whether or not prohibited medication had been taken. Data collected after discontinuing treatment up to week 16 will not be used in the primary efficacy analysis but used in a treatment policy sensitivity analysis. The missing data for patients who discontinued treatment due to lack of efficacy or AEs will be imputed with values centered at the mean baseline value of the treatment group that patients were randomized to. The missing data for patients discontinued treatment due to other reasons will be imputed under missing-at-random assumption using the regression method with adjustment for covariates including treatment group, randomization strata, and baseline score. Intermittently missing data will be imputed using Markov Chain Monte Carlo method.

The primary efficacy variables will be analyzed using a multiple imputation approach with mixed-effect model for repeated measure (MMRM) based on the FAS-substudy with adjustment for missing data due to treatment discontinuation for the reasons of lack of efficacy or AEs assuming the WOMAC scores would on average return to baseline values. Missing data up to week 16 will be imputed 50 times to generate 50 complete data sets by using the SAS procedure PROC MI following the 3 steps below:

- Step 1: The monotone missing pattern is induced by Markov Chain Monte Carlo (MCMC) method in MI procedure using seed number [REDACTED]
- Step 2: The missing data at subsequent visits will be imputed using the regression method for the monotone pattern with seed number [REDACTED] and adjustment for covariates including treatment groups, randomization strata, relevant baseline and all values at preceding visits.
- Step 3: The initially missing and now imputed data for patients discontinued from the study treatment due to lack of efficacy or AEs will be adjusted to be centered at the mean baseline value for that treatment group, i.e., final imputed score = imputed score under MAR - (mean change from baseline score at the post-baseline time point for the treatment group based on patients on treatment with non-missing data at that time point).

Each imputed data set will be analyzed using the MMRM with terms for baseline score corresponding to the primary efficacy variable (e.g. WOMAC pain subscale score at baseline for the analysis of change from baseline in WOMAC pain subscale score), treatment, randomization strata, visit, and treatment by visit interaction. The MMRM will be performed using the MIXED procedure in the Statistical Analysis System (SAS) with an unstructured covariance matrix to model the within-patient errors. Denominator degrees of freedom will be estimated using Kenward-Roger's approximation.

- The results from the 50 analyses will be combined using Rubin's formulae (PROC MIANALYZE). The least squares mean estimates for the mean change from baseline to week 16, as well as the difference of the estimates between fasinumab and placebo, with the corresponding standard error, p-value and associated 95% confidence interval will be provided.

